## 2 Introduction

The study protocol of the NOn-invasive Vagus nerve stimulation in acute Ischemic Stroke (NOVIS) trial has been previously published. Here we provide a summary and updated statistical analysis plan (SAP) with additional detail regarding the scoring of neuro-images, the handling of missing data, and the planned primary and secondary analyses. This SAP was finalized prior to database lock and commencement of the final analysis. Please note that not all pre-specified analyses outlined in this SAP may be included in the main manuscript, due to word count restrictions.

#### 2.1 Research questions

The primary objective is to investigate whether treatment with non-invasive vagus nerve stimulation (nVNS) in addition to standard treatment results in smaller infarct volumes in acute ischemic stroke patients compared with those receiving standard treatment alone. Secondary objectives include assessing the feasibility and tolerability of nVNS, its effect on penumbral recovery, clinical outcomes, and the occurrence of seizures, depression and headache after ischemic stroke. Furthermore, overall survival was added as a secondary objective following the publication of the original protocol.

# 3 Study methods

## 3.1 Trial design

NOVIS is a prospective randomized clinical trial with blinded outcome assessment (PROBE design). Patients are recruited from the stroke unit of the Leiden University Medical Center (LUMC).

#### 3.2 Randomization

150 patients are randomized on a 1:1 basis to nVNS on top of best medical practice or best medical practice alone (including intravenous thrombolysis (IVT) and/or endovascular treatment (EVT)). Randomization is performed with Castor (castoredc.com) and is without stratification.

#### 3.3 Blinding

Patients and investigators are not blinded to treatment allocation due to the nature of the intervention. The primary endpoint will be assessed by two experienced neuroradiologists who are blinded to treatment allocation. The 90-day modified Rankin Scale (mRS) will be assessed by a trained research nurse blinded to treatment allocation.

# 4 Trial population

#### 4.1 Inclusion criteria

- Ischemic stroke comprising the supratentorial region
- Age 18 years or over
- NIHSS 1 or higher
- Perfusion deficit on the admission CT perfusion scan; the penumbra must comprise at least 1/3 of the total ischemic area (ischemic core and penumbra)
- The infarct has to comprise the supratentorial region
- Treatment has to start within 12 hours after stroke onset
- Patients or their legal representatives need to sign informed consent

#### 4.2 Exclusion criteria

- Life expectancy less than three months
- Pre-stroke mRS 3 or higher
- Contraindication for contrast CT agents
- Contraindications for nVNS:
  - An active implantable medical device such as a pacemaker, deep brain stimulator, or any implanted electronic device
  - Symptomatic stenosis or dissection of the carotid artery (in these patients the other side will be stimulated unless a significant stenosis or dissection on the other side is present as well)
  - Structural abnormality e.g. lymphadenopathy, previous surgery or abnormal anatomy (in these patients the other side will be stimulated)
  - o Metal cervical spine hardware or metallic implant near the stimulation site
  - Cervical vagotomy (in these patients the other side will be stimulated)
  - Pregnancy

#### 4.3 Patient selection – flow chart

All consecutive patients of 18 years or older presenting on the emergency department of the LUMC and subsequently admitted to the stroke unit with an ischemic stroke and time of onset or time last seen well less than 12 hours ago will be screened for eligibility. A flow chart will be made showing all in- and excluded patients and the reasons for exclusion.

# 5 Trial endpoints

#### 5.1 Primary endpoint

Infarct volume on day 5 on MRI among those who are alive.

#### 5.2 Secondary endpoints

- Feasibility; defined as more than 75% of the nVNS treated patients completing treatment for five days or until discharge
- Tolerability; defined as less than 10% of the patients treated with nVNS having to abort treatment due to side effects
- Proportion of patients in whom <50% of the penumbra turned into ischemic core on noncontrast CT on day 3
- Clinical outcome (modified Rankin Scale, mRS) on day 90
- Occurrence of seizures or headache in the first 90 days
- Symptoms of depression, quality of life and cognitive status on day 90
- Overall survival in the first 90 days added after protocol publication

Two of the secondary endpoints mentioned in the publication of the study protocol are removed:

- Degree of blood-brain barrier leakage on day three measured with CT perfusion removed due to the inability to reliably quantify this parameter.
- NIHSS on day 5 or on day of discharge if earlier removed because it was considered not to have added value in addition to the radiological outcome and the 90-day clinical outcome.

#### 5.3 Assessment of endpoints

Infarct volumes on MRI will be calculated by manually tracing hyperintense areas on the Diffusion-Weighted Imaging (DWI) sequence using MeVisLab version 3.4.4. Assessments will be done independently by two trained neuro-radiologists blinded to all patient information except for the side of the ischemic stroke. The average infarct volume of the two ratings will be used as the final infarct volume. A Bland-Altman plot will be made to describe interrater agreement. In case of substantial discrepancies between the two assessments the two raters will review their ratings and will trace the final infarct volume together in a consensus meeting.

Perfusion deficits (penumbra and core volumes) will be quantified using automated software (RAPID, iSchemaView).

The 90-day modified Rankin Scale (mRS) will be assessed with a telephone interview by a trained research nurse blinded to treatment allocation.

Symptoms of depression on day 90 will be assessed using the hospital anxiety and depression scale (HADS) questionnaire, quality of life with the EQ-5D and EQ VAS questionnaires, and cognitive status using the Telephone Interview for Cognitive Status (TICS) questionnaire. All questionnaires will be conducted by trained research personnel not blinded to treatment allocation.

## 6 Statistical analysis

#### 6.1 Baseline Characteristics

For continuous variables, the mean and standard deviation (SD), or median and interquartile range (IQR) will be reported in both groups, whichever is appropriate. For discrete variables, the number of subjects in each category and the percentage based on the amount of subjects without missing values will be reported in each treatment group.

#### 6.2 Primary endpoint analysis

Linear regression analysis will be performed to assess the mean difference (MD) in the final infarct volumes between the two groups with corresponding 95% confidence intervals (CIs). The analysis is based on the intention-to-treat principle. Given the randomized design of the study no adjustments for potential outcome variation will be done with multivariable regression analysis. This decision was made after protocol publication. Instead, a sensitivity analysis will be performed with age, NIHSS at randomization and baseline infarct core on CTP as pre-specified covariates.

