### 6.3 Secondary endpoint analyses

Secondary endpoints will be compared using t-tests for continuous variables and chi-square tests for dichotomous variables. Feasibility and tolerability of nVNS will be assessed binary as "reached" or "not reached". Overall survival in the first 90 days will be assessed using a Kaplan-Meier estimator. See table for the method of analysis of the other secondary endpoints. For all secondary analyses, no adjustments will be made unless age, NIHSS at randomization and/or baseline infarct core on CTP appear to be unbalanced between the two treatment groups. Effect estimates are expressed as MD or (common) odds ratios (OR) with 95% confidence intervals (CI).

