## 7 Missing data and death

For all variables the proportion of missing values will be reported. For the primary endpoint, missing infarct volumes among those patients who are alive on day 5 will be imputed using a model containing the following information: NIHSS at randomization, baseline infarct core volume on CTP, infarct volume on NCCT on day 3 (if available), infarct volume on NCCT on day 5 (if available instead of MRI), treatment with IVT and/or EVT, TICI score post EVT, discharge before day 5, and death after day 5. We will use multiple imputation to generate 10 imputed datasets.

In case of missing questionnaires, these patients will be excluded from analyses on secondary endpoints regarding 90 day follow up. Furthermore, a subanalysis using the lowest and the highest values on the various scales will be conducted.

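### The randomised design is no reason to leave the primary model unadjusted: precision is given up on covariates the SAP has already fixed

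*SAP*

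**What the plan says.** The primary endpoint (SAP section 5.1) is "Infarct volume on day 5 on MRI among those who are alive". Section 6.2 analyses it by linear regression, reporting the mean difference with a 95% confidence interval. On covariates it says: "Given the randomized design of the study no adjustments for potential outcome variation will be done with multivariable regression analysis". It adds that this was decided after the protocol was published, and continues: "Instead, a sensitivity analysis will be performed with age, NIHSS at randomization and baseline infarct core on CTP as pre-specified covariates".

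Other sections bear on the choice:

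- Section 3.2: "150 patients are randomized on a 1:1 basis to nVNS on top of best medical practice or best medical practice alone". On the method: "Randomization is performed with Castor (castoredc.com) and is without stratification".
- Section 6.3, for the secondary endpoints: "no adjustments will be made unless age, NIHSS at randomization and/or baseline infarct core on CTP appear to be unbalanced" between the arms.
- Section 7: missing day-5 volumes in survivors are "imputed using a model containing the following information: NIHSS at randomization, baseline infarct core volume on CTP", followed by later imaging, reperfusion treatment and other items. Age and treatment arm are not in the list.

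No other reason for leaving the primary model unadjusted is given.

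**The concern.** The reason given answers a different question. Randomisation means covariates are not needed to remove confounding. It says nothing about the residual variance, which sets the width of the interval. Baseline severity that predicts final infarct volume stays in the error term of an unadjusted model however well the trial was randomised. Since allocation is unstratified, no prognostic factor is balanced by design either.

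The SAP also treats these covariates as relevant elsewhere. It fixes all three for the sensitivity analysis, adjusts secondary endpoints for the same three if they look unbalanced, and uses two of them to predict missing values of this very endpoint.

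If the covariates explain a useful share of infarct volume, the trial's main conclusion will rest on a wider interval and lower power than the same patients allow. The more precise model would stand only as support. Should the two disagree on significance, the plan gives precedence to the less precise one.

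**Working it through.** **Inputs from the SAP.** 150 patients, 1:1, so n = 75 per arm (section 3.2). Continuous outcome, linear regression, 95% interval (section 6.2), taken as a two-sided 5% test. Three covariates (section 6.2).

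**Inputs that are assumptions.** The SAP gives no SD, effect size, power or R², so the figure of 150 cannot be reproduced. I use an effect of 0.46 SD, because it gives about 80% unadjusted power with 75 per arm, and a range of R² from 0 to 0.5. R² is the share of infarct-volume variance, on the raw scale, explained by the three covariates. To show the effect of the survivors-only restriction, I also use 65 per arm.

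**Formulas** (standard errors in SD units, power from the noncentral t distribution):

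- Unadjusted: SE = √(2/n), df = 2n − 2.
- Adjusted: SE = √[(2/n)(1 − R²)(2n − 3)/(2n − 6)], df = 2n − 5. The last factor is the average cost of chance imbalance in three covariates.
- CI ratio = (adjusted t × SE) / (unadjusted t × SE).
- Equivalent unadjusted sample size = 2n / (CI ratio)².

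**Worked case, n = 75, R² = 0.2.**

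- Unadjusted: SE = √(2/75) = 0.1633. Noncentrality = 0.46/0.1633 = 2.82, df 148, power 79.9%.
- Adjusted: SE = √(0.02667 × 0.8 × 147/144) = 0.1476. Noncentrality = 0.46/0.1476 = 3.12, df 145, power 87.2%.
- CI ratio = (1.9765 × 0.1476)/(1.9761 × 0.1633) = 0.904.
- Equivalent sample size = 150/0.904² ≈ 184.

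**All cases** (unadjusted power is 79.9% with 75 per arm and 74.0% with 65 per arm):

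| Assumed R² | CI ratio, 75 per arm | Adjusted power, 75 per arm | Equivalent unadjusted N | Adjusted power, 65 per arm |
|---|---|---|---|---|
| 0 | 1.011 | 79.1% | 147 | 73.0% |
| 0.1 | 0.959 | 83.1% | 163 | 77.3% |
| 0.2 | 0.904 | 87.2% | 184 | 82.0% |
| 0.3 | 0.845 | 91.2% | 210 | 86.7% |
| 0.5 | 0.715 | 97.5% | 294 | 95.3% |

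**Break-even.** Adjustment pays once (1 − R²) × 147/144 falls below 1, so R² above 1 − 144/147 ≈ 0.02.

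**Simulation checks** (75 per arm, normal covariates and errors). With 20,000 trials per setting, adjusted power was 79.3%, 83.4%, 86.9%, 90.8% and 97.6% for the five R² values, in line with the table. A separate run of 4,000 trials per setting put type I error between 4.6% and 5.4% for both models.

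**The case against.** The strongest case against is that nothing is invalid and nothing is missing. An unadjusted primary analysis with an adjusted sensitivity analysis is a recognised convention, and the adjusted model is already written down. That is true, and it limits the point to efficiency. It does not rescue the stated reason, and the trial's conclusion would still rest on the less precise estimate.

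**The gain is assumed, not shown.** This stands. At R² = 0.1 the gain is modest, and nothing in the SAP supports 0.5. Use in an imputation model does not prove a high R², and the section 6.3 trigger concerns imbalance rather than precision. The advice needs only an R² above about 0.02.

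**Infarct volumes are usually skewed**, so a good relation on the log scale may explain less on the raw scale. This also stands as a caution. An illustrative check used log-normal volumes, 75 per arm, covariates acting on log volume with R² 0.3 there, and an additive 0.46 SD effect. With a log-SD of 1.0, the raw R² was about 0.17, the interval 9% narrower, and power rose from 82% to 87%. With a log-SD of 1.5, the figures were about 0.08, 6%, and 88% to 89%. The gain shrinks but stays positive.

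**Randomisation does not by itself guarantee an unbiased comparison here**, because the endpoint is restricted to survivors and some volumes are imputed. This is correct, but both models carry that caveat, so it does not favour the unadjusted one.

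**A further change of the primary model has a credibility cost.** The choice has already changed once since the protocol was published, and investigators are not blinded (section 3.3). This is fair. The change is defensible only if it is dated before anyone sees results by arm, including the preliminary analysis at soft-lock allowed by section 8.

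**Conclusion.** The concern holds. The randomised design does not justify leaving explainable variance in the primary model, and the SAP already fixes the covariates that would remove some of it. In a linear model without an interaction, adjustment targets the same mean difference, so the question asked is unchanged.

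The potential loss is lopsided. Adjusting costs an interval about 1% wider if the covariates explain nothing. Not adjusting costs an interval about 10% wider than the adjusted one (1/0.904 ≈ 1.11) if R² is 0.2. The figures rest on an assumed 0.46 SD effect, assumed R² values and normal-theory calculations. The true gain cannot be known from the SAP and may sit in the lower part of the range if volumes are strongly skewed. This is a change the sponsor should make; it is not a flaw that invalidates the planned test.

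**What to change.** Before any analysis by arm:

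1. In section 6.2, make the primary analysis the linear model with treatment arm, age, NIHSS at randomization and baseline CTP core. Report the unadjusted mean difference as the sensitivity analysis. Record the date and reason, and delete the appeal to the randomised design.
2. In section 7, add age to the imputation model, and treatment arm if it is not already included, so that the model contains every variable of the primary analysis. Age is already in the planned sensitivity model, so this is needed whichever model is primary.
3. State how a missing covariate value is handled.

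The cost is edits to two sections, three degrees of freedom and a documented further change to the primary model. No new data are needed. Age, an NIHSS score and the admission scan all enter the eligibility check in section 4.1, which requires "Perfusion deficit on the admission CT perfusion scan", so few values should be missing. That section does not say when the NIHSS is taken, so confirm that the value at randomization is recorded for everyone.

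### Reperfusion treatment (IVT/EVT) is unstratified background care but enters no outcome model, so the only adjusted check on the primary result cannot address a chance imbalance in it

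*SAP*

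**What the plan says.** - **Design (SAP 3.2).** "150 patients are randomized on a 1:1 basis to nVNS on top of best medical practice". The comparator is "best medical practice alone (including intravenous thrombolysis (IVT) and/or endovascular treatment (EVT", so both arms mix patients with no reperfusion treatment, IVT, EVT or both. "Randomization is performed with Castor (castoredc.com) and is without stratification".
- **Primary analysis (SAP 6.2).** The main model has no covariates: "Given the randomized design of the study no adjustments for potential outcome variation will be done with multivariable regression analysis". In its place, "a sensitivity analysis will be performed with age, NIHSS at randomization and baseline infarct core on CTP as pre-specified covariates".
- **Secondary analyses (SAP 6.3 and the Table).** "no adjustments will be made unless age, NIHSS at randomization and/or baseline infarct core on CTP appear to be unbalanced". The Table names a model for each endpoint and no covariates. The penumbra endpoint, "Proportion of patients in whom <50% of the penumbra turned into ischemic core on noncontrast CT on day 3", gets a binary logistic model.
- **Imputation (SAP 7).** The model for missing day-5 volumes includes "treatment with IVT and/or EVT, TICI score post EVT". Apart from the description of background care in 3.2, this is the only place where reperfusion treatment appears.
- **Not stated.** The SAP gives no IVT or EVT rate and no effect of either on any endpoint. It does not say whether IVT or EVT is given or decided before randomisation.

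**The concern.** Section 6.2 replaces adjustment of the primary model by a sensitivity analysis, so that analysis is the plan's only pre-specified guard on the primary result against prognostic imbalance. Its three covariates describe the patient at entry. None records whether the patient received treatment aimed at reopening the vessel. However large an imbalance in IVT/EVT turned out to be, it would trigger nothing under 6.3 and could not be examined under 6.2.

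The penumbra endpoint is directly exposed. It asks whether tissue at risk on admission became core by day 3, and reperfusion treatment plausibly acts on exactly that. It also lacks what the primary endpoint has, an adjusted analysis that is run regardless of observed balance.

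Two things are at stake: precision, and how far the result can be trusted given the imbalance that actually occurs. If reperfusion is added only after an imbalance has been seen, the analysis is post hoc. The question is which covariates the set lacks, not whether the primary model should be adjusted.

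**Working it through.** The SAP states no figure on this point, so there is none to reproduce. From the documents come 150 patients at 1:1, hence 75 per arm, and 95% confidence intervals (two-sided 5% is assumed). Every reperfusion share and effect below is an assumption.

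**1. How large a chance imbalance is likely.** For an overall share p, SE of the between-arm difference = √(2p(1−p)/75).

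| p | SE (points) | 1.96 × SE (points) | P(10 points or more), normal | P(10 points or more), exact |
|---|---|---|---|---|
| 20% | 6.5 | 13 | 13% | 15% |
| 40% | 8.0 | 16 | 21% | 24% |
| 50% | 8.2 | 16 | 22% | 19% |

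The exact column is hypergeometric. It does not rise smoothly, because only whole patients can be imbalanced. Taking both methods, the range is about 13-24%. For 15 points or more the exact probability is 2-7%.

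**2. What a 10-point imbalance does to the penumbra comparison.** With no nVNS effect and success rates s₁ (treated) and s₀ (not treated), the expected success in the two arms is s₀ + (s₁−s₀)(p ± 0.05).
- s₁ = 60%, s₀ = 40%, p = 50%: 51% v 49%. The shift is 2 points and the OR 1.08. SE = √((0.51×0.49 + 0.49×0.51)/75) = 8.2 points. Ratio 0.25 SE.
- s₁ = 80%, s₀ = 30%, p = 50%: 57.5% v 52.5%. The shift is 5 points and the OR (0.575/0.425)/(0.525/0.475) = 1.22. SE = 8.1 points. Ratio 0.6 SE.

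At 15 points the shift is 3-7.5 points, about 0.4-0.9 SE.

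**3. The same for infarct volume.** The SE of the mean difference is √(2/75) = 0.163 SD. With an assumed reperfusion effect of 0.3-0.8 SD, a 10-point imbalance shifts the difference by 0.03-0.08 SD, that is 0.03/0.163 to 0.08/0.163, or about 0.2-0.5 SE. This overlaps the penumbra range.

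**4. Precision for infarct volume.** If the term explains a further 5-30% of residual variance, the SE is multiplied by √(1−R²): √0.95 = 0.975 to √0.70 = 0.837. A design with 80% power (difference 0.457 SD) would move to 82-92%.

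**5. Power for the penumbra endpoint.** Logistic simulation, 150 patients, conditional OR 2.5, 1,500 replicates:

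| Success, treated v not | Share treated | Without term | With term |
|---|---|---|---|
| 85% v 45% | 40% | 60% | 66% |
| 90% v 30% | 50% | 42% | 57% |
| 70% v 50% | 30% | 74% | 74% |

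**6. False positives with no nVNS effect.** Over all randomisations, in the same three scenarios, the unadjusted model rejects in 5.7%, 4.7% and 4.7% of trials, and the model with the term in 5.4%, 4.3% and 4.4%. Given a particular imbalance the picture changes:

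| Treated, of 75 v of 75 | Imbalance (points) | Success, treated v not | Unadjusted | With term |
|---|---|---|---|---|
| 34 v 26 | 10.7 | 85% v 45% | 6.7% | 5.8% |
| 36 v 24 | 16.0 | 85% v 45% | 11.5% | 5.0% |
| 43 v 32 | 14.7 | 90% v 30% | 14.7% | 4.9% |

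**The case against.** **The unadjusted comparison is valid as it stands.** A reader might infer that a chance excess of EVT in one arm biases the result and would pass for an nVNS effect. The documents do not support that. Under randomisation the unadjusted estimate is unbiased, its interval already allows for chance imbalance, and the overall false-positive rate stays near 5% (step 6). This stands. What is left is precision and accuracy given the imbalance observed.

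**The imputation list proves nothing.** A reader might see a contradiction between sections 6.2 and 7. There is none. An imputation model should hold predictors of the missing value, including later events: the same list has the day-3 CT volume, discharge before day 5 and death after day 5. Age is an outcome covariate but is not in that list. This stands too. The list shows only that the sponsor regards reperfusion treatment as informative about infarct volume and holds the variable.

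**The penumbra endpoint is not shown to be the worst affected.** That ranking is tempting, because the endpoint concerns tissue that reperfusion may save. But the SAP ranks nothing, all secondary endpoints share one adjustment rule, and the illustrative ranges overlap (0.25-0.6 SE against 0.2-0.5 SE).

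**Three covariates in 150 patients is a coherent choice, and the gains rest on assumed inputs.** True: one power scenario shows no gain, and the 15-point gain needs a very strong reperfusion effect. The choice still leaves out a background treatment that the SAP itself treats as informative, and gives no reason.

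**The remedy depends on timing that the SAP does not state.** This stands, and it limits the fix. Treatment decided is also not the same as a vessel reopened, so the term captures only part of the variation.

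**Conclusion.** The point holds as a gap in the pre-specified covariates, not as an error in the primary comparison. Reperfusion treatment is unstratified and absent from every outcome model and from the imbalance rule. The unadjusted estimates and intervals remain valid. The plan gives up precision, and its one adjusted check on the primary result cannot address a chance imbalance in reperfusion treatment. The penumbra endpoint is directly, but not demonstrably most, exposed.

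The size is modest. An imbalance of 10 points or more has a probability of about 13-24%, and at 10 points the estimate moves by about 0.2-0.6 SE. Imbalances near 15 points, at which the conditional false-positive rate could reach 11-15%, are uncommon (2-7%). The power gain for the penumbra endpoint lies between nil and about 15 points. All of this rests on assumed shares of 20-50% treated and on assumed effects of treatment. The SAP supplies neither.

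**What to change.** - **SAP 6.2.** Add a reperfusion-treatment term (none / IVT only / EVT with or without IVT) to the pre-specified covariates of the sensitivity analysis. Code it only from treatment given or decided before randomisation, and state that rule.
- **SAP 6.3 and the Table.** Pre-specify the same term in the logistic model for the penumbra endpoint, whatever the observed balance.
- **TICI.** Leave it out of the outcome models unless EVT is documented as completed before randomisation. It can stay in the imputation model.
- **Timing of the change.** Make it before outcomes are compared by arm. Otherwise label the analysis post hoc.

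The cost is SAP wording, since section 7 already relies on IVT/EVT data, provided that their timing relative to randomisation is recorded. The term uses two degrees of freedom in 150 patients. The penumbra odds ratio becomes conditional on reperfusion treatment and will differ somewhat from the unadjusted one. The unadjusted primary model is unchanged.

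### Baseline penumbra volume is required for entry and measured with core, but is a predictor in neither the adjusted sensitivity analysis nor the imputation model for infarct volume

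*SAP*

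**What the plan says.** **Entry and measurement.** SAP 4.1 admits patients with a perfusion deficit in which "the penumbra must comprise at least 1/3 of the total ischemic area (ischemic core and penumbra". SAP 5.3 states that "Perfusion deficits (penumbra and core volumes) will be quantified using automated software". Both volumes therefore come from one processing step.

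**Primary analysis.** SAP 6.2 compares infarct volumes by linear regression, and "no adjustments for potential outcome variation will be done with multivariable regression analysis".

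**Sensitivity analysis.** The same section adds an adjusted analysis with "age, NIHSS at randomization and baseline infarct core on CTP as pre-specified covariates".

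**Imputation.** SAP 7 imputes missing day-5 volumes in patients alive on day 5. The list of predictors begins "NIHSS at randomization, baseline infarct core volume on CTP, infarct volume on NCCT on day 3 (if available" and continues with a day-5 NCCT volume where it replaces MRI, IVT and/or EVT, TICI after EVT, early discharge and death after day 5.

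**Randomisation.** SAP 3.2 allocates 150 patients 1:1 without stratification.

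Penumbra volume is on neither predictor list. Elsewhere it appears in the entry ratio and in the definition of the day-3 secondary endpoint (SAP 5.2).

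**The concern.** Penumbra is the tissue that may still become infarct, and SAP 5.2 itself defines an endpoint by how much of it turns into core. Of the two baseline perfusion volumes, the models use the one already counted as lost and omit the one whose fate is open.

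Two things are at stake. First, the adjusted analysis is there to show whether the result holds once prognostic differences are taken into account. If the arms differ by chance in penumbra, it can correct only the part that age, NIHSS and core happen to carry. Second, imputed volumes enter the primary estimate. The imputation model includes treatments and a reperfusion grade that bear on whether penumbra is saved, but not how much penumbra there was.

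**Working it through.** **1. Does core stand in for penumbra?** Let C be core and P penumbra. The entry rule is P/(C + P) ≥ 1/3. Then 3P ≥ C + P, so P ≥ 0.5 × C, with no upper limit. A patient with a 10 mL core is eligible with 5 mL of penumbra (5/15 = 0.33) and also with 120 mL (120/130 = 0.92). The rule does not standardise the volume at risk, and core does not determine it.

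**2. Predictors side by side.**

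| Model | Predictors listed | Baseline perfusion volume |
|---|---|---|
| 6.2 primary | treatment only | none |
| 6.2 sensitivity | treatment, age, NIHSS, core | core |
| 7 imputation | NIHSS, core, NCCT day 3 and day 5 if available, IVT/EVT, TICI, early discharge, death after day 5 | core |

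**3. Chance imbalance.** With 150 patients at 1:1, take 75 per arm. The between-arm difference in mean penumbra has standard deviation √(2/75) = 0.163 in units of the SD of penumbra. Its 95% range is ±1.96 × 0.163 = ±0.32 SD.

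**4. Precision of the adjusted analysis.** The SAP gives no volumes, SDs or correlations, so there is no stated figure to reproduce. Let r be the partial correlation of penumbra with day-5 volume, given age, NIHSS and core. Adding penumbra multiplies the residual variance by 1 − r². The assumed range is r = 0.3 to 0.5.

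- r = 0.3: 1 − 0.09 = 0.91, a 9% fall. The standard error is multiplied by √0.91 = 0.954.
- r = 0.5: 1 − 0.25 = 0.75, a 25% fall. The standard error is multiplied by √0.75 = 0.866.

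The cost is one residual degree of freedom. With an intercept, treatment and three covariates there are at most 150 − 5 = 145, and a fourth covariate leaves 144. The variance penalty is about 145/144 = 1.007, or 0.7%.

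**5. What an imbalance would do.** Measure the imbalance in the part of penumbra that the other three covariates do not predict, and the outcome in residual SDs. An imbalance of 0.32 SD then moves the adjusted difference by r × 0.32, which is 0.3 × 0.32 = 0.096 to 0.5 × 0.32 = 0.16 residual SD. For scale, at an assumed two-sided 5% level and 80% power, 75 per arm can detect (1.960 + 0.842) × 0.163 = 0.457 SD. The movement is 0.096/0.457 = 21% to 0.16/0.457 = 35% of that.

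**6. Imputation.** If a fraction m of an arm is imputed, the arm mean is (1 − m) × observed mean + m × imputed mean. An error e in the imputed mean moves the arm mean by m × e, and equal errors in both arms with equal m cancel. The SAP states neither m nor how many imputed patients will lack both NCCT volumes, so no figure can be given. For those patients the prediction rests on NIHSS, core, IVT/EVT, TICI, early discharge and later death. If penumbra predicts both a missing MRI and infarct volume given that list, missing at random given that list does not hold.

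**The case against.** **It is a choice of covariates, not an error.** The three listed covariates are plausible and pre-specified, and a trial need not adjust for the variable it selects on. That stands as far as contradiction goes: the SAP contradicts nothing here. But the omitted measure is already collected, is not determined by core, and can change both the sensitivity result and the imputed volumes. That makes it more than taste.

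**Other variables carry part of the information.** The sensitivity analysis also has age and NIHSS. The imputation also has NIHSS, IVT/EVT, TICI and follow-up NCCT volumes. A day-3 or day-5 volume measures growth that has already happened, so penumbra may add little where one exists. This stands, and it confines the imputation point mainly to patients with neither scan.

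**Stronger readings that the SAP does not support.**

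- *The primary comparison is biased.* A reader might infer this from the imbalance figures. Under randomisation the unadjusted estimate is unbiased, and its confidence interval already allows for chance imbalance in any baseline variable.
- *The trial loses patients' worth of information.* The range in step 4 corresponds to 150/0.91 = 165 to 150/0.75 = 200 patients, but only in the adjusted analysis and only under assumed correlations. The primary model leaves core, age and NIHSS unadjusted too. Apart from imputed values, adding penumbra to the sensitivity analysis does not touch it.
- *Penumbra is the only tissue that nVNS could save.* The SAP does not say so; it lists penumbral recovery among its secondary objectives (section 2.1).
- *The day-3 penumbra endpoint should be adjusted for baseline penumbra.* That would adjust an endpoint for its own denominator, change the meaning of its odds ratio, and depart from SAP 6.3, under which "no adjustments will be made unless age, NIHSS at randomization and/or baseline infarct core on CTP appear to be unbalanced". It does not follow from this point.

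**Conclusion.** The point holds as a gap in two pre-specified models. Core is the only baseline perfusion volume in the 6.2 sensitivity analysis and in the section 7 imputation, although penumbra is required for entry, quantified with core, and bounded by it only from below. There are three consequences: some loss of precision in the adjusted analysis, an adjusted analysis that cannot directly address a chance imbalance in penumbra, and a less plausible missing-at-random assumption, chiefly for patients without an NCCT volume on day 3 or day 5.

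The direction is clear but the size is not. The 9% to 25% fall in residual variance rests wholly on an assumed partial correlation of 0.3 to 0.5. The effect on the imputed primary estimate depends on the amount of missing data, which the SAP does not give. The point merits correction because it is nearly free, but it does not undermine the randomised comparison.

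**What to change.** 1. In SAP 6.2, add baseline CTP penumbra volume (mL, from RAPID) as a fourth pre-specified covariate of the sensitivity analysis, and state the scale on which core and penumbra enter. With core in a linear model on the mL scale, entering total volume (core + penumbra) instead gives the same fit.
2. In SAP 7, add the same variable to the imputation predictors. The two changes belong together: imputing without a covariate that the analysis model uses would weaken its estimated association with the outcome.
3. Make both changes before any analysis at soft-lock, which SAP 8 allows once the last primary outcome is recorded. If results have already been seen, report the additions as post hoc.

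The unadjusted primary model and the day-3 endpoint analysis stay as they are.

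**Cost:** two lines of SAP text and one degree of freedom in each model. No new data collection should be needed, since eligibility required the measurement and the software returns it with core.
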